# 8. GENERAL ISSUES FOR STATISTICAL ANALYSES

# 8.1 Adjustment for Covariates

The log-transformed antibody titer at each timepoint will be analyzed using an Analysis of Variance (ANOVA) which includes the vaccine-group effect and a center effect (see section 8.3). Summary tables will show adjusted GMTs and adjusted ratios of GMTs for each vaccine group.

Binary data tables will show unadjusted percentages and "between-group" differences.

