8.3.7 Subgroups

Analysis of the primary objective will be repeated and stratified by country, gender and race using the FAS and the PPS.

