8.4.2.2.3 Statistical Methods

For each N. meningitidis serogroup B test strain (M14459, M07-0241084, 96217 and NZ89/254) and for each of the serogroups A, C, W nd Y the percentages of subjects with HT-hSBA titers \geq LLOQ and the corresponding exact two-sided 95% CIs based on the Clopper-Pearson method will be calculated at Day 1 (i.e. approximately 24 months after the last meningococcal vaccination in study V102_15 for follow-on subjects, and Day 1 for naïve subjects). The CIs for the rate difference will be constructed using the method of Miettinen and Nurminen (Miettinen and Nurminen, 1985).

The hSBA titers at visit 1 Day 1 for each study group will be logarithmically transformed (base10) to fulfil the normal distribution assumption. For each N. meningitidis serogroup B test strain (M14459, M07-0241084, 96217, and NZ98/254) and serogroups A, C, W, and Y, the GMTs will be calculated with their associated two-sided 95% CIs, by exponentiating the corresponding log-transformed means and their 95% CIs obtained from the Analysis of Variance (ANOVA) model with study center included as an independent variable. Between-group ratios of GMTs will be calculated by exponentiating the between-group difference in the least square means of the log-transformed titers and the 95% CIs. In addition, a reverse cumulative distribution plot of each measure will be created.

(Amended 4 April 2018)

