# 10.1 Demographics

Age, height, weight, body mass index at enrolment in this extension study will be summarized by reporting the mean, standard deviation, median and range, and will be calculated by vaccine group and overall.

The frequencies and percentages of subjects by sex, country, age categories (for posting), ethnic origin, entry criteria fulfilled will be presented by vaccine group and overall. Demographic data will be tabulated for the All Enrolled, FAS persistence, PPS persistence, and Safety sets.

Demography and baseline characteristics at time of enrolment in parent study (V102\_15) will also be reported (by vaccine group), in the subset of subjects from Poland and Finland, in the 4 vaccine groups of interest (ABCWY\_0\_2, ABCWY\_0\_6, ABCWY\_0\_2\_6, B\_0\_2), separately for subjects subsequently enrolled and not enrolled in this current extension study (V102\_15E1).

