#### Statistical Methods

For each *N. meningitidis* serogroup B test strain (NZ98/254, M14459, M07-0241084 and 96217) the percentages of subjects with HT-hSBA titers ≥ LLOQ and the corresponding exact two-sided 95% CIs based on Clopper-Pearson method will be calculated at Day 1, Day 6 and Day 31 (follow-on) / Day 1, Day 66 and Day 91 (naive). Percentages and the

<sup>8 For subjects with prevaccination hSBA titers < LLOQ, a post-vaccination hSBA  $\geq$  4 times the LLOQ; for subjects with prevaccination hSBA titers  $\geq$  LLOQ, an increase of at least 4 times the prevaccination hSBA.  Serogroup B test strains to be used in the study: NZ98/254 (PorA), M14459 (fHbp), M07-0241084 (NHBA) and 96217 (NadA).

corresponding CIs will also be computed for subjects who are positive for at least one test strain, at least two test strains, at least three test strains, and all four test strains. The CIs for the rate difference will be constructed using the method of Miettinen and Nurminen (Miettinen and Nurminen, 1985).

The hSBA titers at each visit for each study group will be logarithmically transformed (base10) to fulfill the normal distribution assumption. For each *N. meningitidis* serogroup B test strain (NZ98/254, M14459, M07-0241084 and 96217), the GMTs and GMRs (post vaccination / pre-vaccination) will be calculated with their associated two-sided 95% CIs, by exponentiating the corresponding log-transformed means and their 95% CIs. Percentages of subjects with four-fold titer rise, the percentages of subjects with hSBA titers ≥ LLOQ and the corresponding exact two-sided 95% CIs based on the Clopper-Pearson method against these strains will be calculated for each study group at Day 1, Day 6 and Day 31 (follow-on) / Day 1, Day 66 and Day 91 (naive). The ratio of GMTs and GMRs between the two study groups and the corresponding CI will be constructed by exponentiating the mean difference and the confidence limits in log10 (titer), using ANOVA with study center included as an independent variable. The CIs for the rate difference will be constructed using the method of Miettinen and Nurminen. In addition, a reverse cumulative distribution plot of each measure will be created.

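### Age is in no model or subgroup of the non-randomised primary comparison, although similar age is part of what makes the naive group a control (low severity)

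*SAP*

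**What the plan says.** **Design.** Protocol 3.1 keeps follow-on subjects in their parent-study groups and randomises only naive subjects, 1:1 between the two vaccines. The naive group is to be vaccine-naive and of similar age, roughly 12 to 20 years, so that it can act as the persistence control. Protocol 4.1 repeats that approximate range as the naive entry criterion. Naive enrolment is made proportional by country; no age matching, quota or stratum is described.

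**GMTs.** Protocol 8.4.2.2.3 takes the Day 1 GMTs and their ratios from an "Analysis of Variance (ANOVA) model with study center included as an independent variable". SAP 8.1 describes the same model as one "which includes the vaccine-group effect and a center effect". The protocol synopsis says that the ANOVA is there to deal with imbalance in explanatory variables, but does not name them.

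**Rates.** For percentages at or above LLOQ, "The CIs for the rate difference will be constructed using the method of Miettinen and Nurminen" (Protocol 8.4.2.2.3). SAP 8.1 adds: "Binary data tables will show unadjusted percentages".

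**Subgroups.** "Analysis of the primary objective will be repeated and stratified by country, gender and race using the FAS and the PPS" (Protocol 8.3.7, repeated in SAP 8.6).

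**Where age does appear.** SAP 10.1: "Age, height, weight, body mass index at enrolment in this extension study will be summarized" by vaccine group, and "Demographic data will be tabulated for the All Enrolled, FAS persistence, PPS persistence, and Safety sets".

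**The concern.** Randomisation does not balance age between follow-on and naive subjects, so comparability on age rests on an approximate range nine years wide (12 to under 21). If the two populations differ in mean age within that range, and if background titres vary with age, part of any GMT ratio or rate difference reflects age and not persistence of vaccine antibody. The demographic tables would show the imbalance, but no planned analysis would remove it. An age adjustment chosen after titres are known would be open to the charge that the results drove it.

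The plan adjusts GMTs for centre and repeats the analysis by country, a factor that enrolment already balances. It leaves out the demographic factor that the protocol itself names as a condition for the control.

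**Working it through.** **1. Where age could enter.** There is no plan figure to reproduce: Protocol 8.5 (sample size) reads as not applicable, and SAP 5 refers back to it.

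| Element | Factors named | Age? |
|---|---|---|
| Day 1 GMT ANOVA (Protocol 8.4.2.2.3, SAP 8.1) | group, centre | no |
| Day 1 rate difference (Protocol 8.4.2.2.3, SAP 8.1) | none | no |
| Subgroups (Protocol 8.3.7, SAP 8.6) | country, gender, race | no |
| Balancing of naive enrolment (Protocol 3.1) | country | no |
| Demographic tables (SAP 10.1) | age and others, by group | yes, descriptive |

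**2. Number of estimates.** By Protocol 8.1.1.2, serogroups A, C, W and Y apply to the MenABCWY groups only. Four follow-on groups × 4 B strains + 3 groups × 4 serogroups = 28 rate differences and 28 GMT ratios.

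**3. Nominal ages at Day 1.** Parent entry is at 10 through 18 years (Protocol 1.1), read as 10 to under 19. Add 2 or 6 months to the last dose, then 24 months with a window of −1/+3 (Protocol 3.1), that is 23 to 27 months.
- 0,2 schedules: 10 + 25/12 = 12.1 to under 19 + 29/12 = 21.4 years.
- 0,6 and 0,2,6 schedules: 10 + 29/12 = 12.4 to under 19 + 33/12 = 21.75 years.
- Naive subjects: 12 to under 21 years.

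The ends of the range shift by between 2 + 23 − 24 = 1 month and 6 + 27 − 24 = 9 months. The 9-month end applies only if follow-on subjects have no upper age limit. The synopsis and Protocol 3.1 give 12-20 years for the whole study, while Protocol 4.1 lists no limit for follow-on subjects. These are shifts of ranges; the mean gap is not known.

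**4. Rate difference, on assumptions.** Assumed: naive rate 30%, true difference 20 points, age slope 1 to 3 points per year, 100 follow-on subjects against 100 or 200 naive.
- Bias = slope × gap. At 2 to 6 months: 1 × 0.17 = 0.2 to 3 × 0.5 = 1.5 points. At 9 months: 1 × 0.75 = 0.75 to 3 × 0.75 = 2.25 points.
- Wald half-width = 1.96 × √(0.5×0.5/100 + 0.3×0.7/n) = 13.3 points (n = 100) or 11.7 points (n = 200). Simulated Miettinen-Nurminen half-widths are 13.2 and 11.5 points.
- Simulated crude coverage (6,000 runs per scenario, age SD 2 years) is 94.5 to 95.1% at gaps of 0.33 to 0.5 year. Stratifying at age 16 gives 94.4 to 95.5%, which is no material change.
- At a 1-year gap, for which the documents give no basis, the bias is 1 to 3 points and crude coverage 92.5 to 95.3%.

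**5. GMT ratio, on assumptions.** Assumed slope 0.02 to 0.06 log10 per year.
- Bias factor = 10^(slope × gap): 10^(0.02×0.17) = 1.01 to 10^(0.06×0.5) = 1.07. At 9 months: 10^(0.02×0.75) = 1.04 to 10^(0.06×0.75) = 1.11.
- CI factor = 10^(1.96 × SD × √(1/100 + 1/n)) = 1.32 (SD 0.5, n = 200) to 1.56 (SD 0.7, n = 100).
- In simulation (3,000 runs, 10 assumed centres, gap 0.33 year) the bias factor is 1.015 to 1.049 without age in the model and 0.998 to 1.003 with it. Coverage is 93.5 to 95.2% and 94.1 to 95.3%.

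**6. Larger assumed inputs.** At 0.05 log10 per year and a 1-year gap, with 100 against 200 and SD 0.4 to 0.6, the factor is 10^0.05 = 1.12 and coverage 83 to 90%. Nothing in the documents supports or excludes such values.

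**The case against.** The strongest reply is that this is a matter of preference. The study has no hypotheses and no success criteria for the primary objective (Protocol 8.4.2.2.1 and 8.2.1.2). Age is tabulated in the very sets used for persistence. At gaps up to half a year the assumed bias is a small fraction of the CI half-width, and coverage hardly moves. Both a steeper slope and a wider gap have to be assumed before it does. All of this stands, and it sets the severity. It does not remove the point, because in a descriptive study the estimates and intervals are the whole result, and range shifts do not bound the mean gap.

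A second reply is that the synopsis already has the ANOVA handle unbalanced explanatory variables. A reader might infer that age is among them. The methods sections do not support that: besides group, centre is the only factor named, also for the later visits ("using ANOVA with study center included as an independent variable", SAP 11.3).

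A third reply is that changing the GMT model while keeping the crude rate difference is inconsistent. The two measures start from different places. The GMTs are already adjusted least squares means, so age is one more term. The rate difference is unadjusted by design, so an adjusted version fits better as supportive.

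**Conclusion.** The point holds at low severity. Age is absent from the GMT model, the rate differences and the subgroups of a non-randomised comparison for which the protocol asks for similar age. An imbalance would be visible but not removed.

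The size cannot be derived from the documents. On the assumed slopes the bias is 0.2 to 1.5 points, or a GMT-ratio factor of 1.01 to 1.07, at gaps of 2 to 6 months. It is up to 2.25 points, or a factor of 1.11, if the mean gap were as large as the greatest range shift. All of these lie well inside the CI half-widths.

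Two stronger readings should be resisted. One is that the plan ignores age: it does not, since age is an entry criterion and is tabulated by group. The other is that the primary estimates are materially biased or their intervals invalid: that needs larger gaps or steeper slopes than anything the documents give. No decision rule or error rate is at stake.

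**What to change.** **GMT ratios.** In SAP 8.1, state that for the Day 1 follow-on versus naive GMT ratios the ANOVA includes age at enrolment (continuous) with vaccine group and centre. The GMTs shown with these ratios are then least squares means at the mean age of the subjects in the model. Name age and centre as the explanatory variables that the synopsis mentions. Protocol 8.4.2.2.3 names only centre, so either align it or record the added covariate in the SAP as a change from the protocol.

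**Rate differences.** Keep the crude Miettinen-Nurminen difference as the main estimate. Add a pre-specified supportive Miettinen-Nurminen difference, stratified by age band at enrolment, for the same Day 1 comparisons. Fix the cut before titres are seen; 16 years, the midpoint of 12-20, is one example. If a band is empty in either group, show only the crude difference.

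**Cost.** SAP wording, a protocol alignment or a recorded change, and one extra line per table. Date of birth is already collected (Protocol 5.1.2). The ANOVA assumes one linear age slope for follow-on and naive subjects. Two bands leave about a third of a linear age bias, and the stratified difference will not equal the subtraction of the displayed percentages.

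In the simulations the stratified half-width is 0.1 to 0.8% wider at gaps up to 0.5 year and 2.0 to 2.5% wider at 1 year. Adding age changes the log GMT-ratio CI width by −2.1% to +0.5% at 0.33 year, and by at most +3.1% at 1 year.

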# 8.2 Handling of Dropouts, Missing Data

First-line analyses will be without missing values.

To minimize the effect of dropouts and missing data the study period will be divided into time intervals for statistical analysis of safety.

# 8.2.1 Safety Data

For unsolicited adverse events, the entire study period will be divided into the following intervals:

For solicited adverse events, the solicited study period 30 min - day 7 will be divided into: 30 min, 6h - day 3, day 4 - day 7, and 6h - day 7.

For each of the intervals the following algorithm will be applied:

- 1. If less than 20% of subjects are without any solicited AE data (i.e., none of the solicited adverse events has been captured) for the respective time interval, then only the Solicited Safety Set pertaining to the interval will be analyzed.
- 2. If 20% or more of subjects are without any solicited AE data, the missing mechanism will be analyzed by vaccine group using a newly created variable indicating whether a subject is missing the respective AE-value or not (1=AE record present; 0=AE record not present).
  - a. If the percentage of missing subjects does not vary significantly between vaccine groups (p>0.05) then 'missing completely at random' (MCAR) is assumed and no further action is required. Data will be analyzed without the missing values.
  - b. If the percentage of missing subjects varies significantly between vaccine group  $(p \le 0.05)$  then 'missing at random' (MAR) is assumed, i.e., the missing mechanism is conditional on the vaccine group. Imputation methods will be applied to reduce

potential bias arising from missing values (if applicable, details will be given in an addendum to the SAP, and results included in Appendix 16.1.9 of the CSR).

For solicited adverse events, imputations will be confined to analyses of any (rather than specific) solicited local adverse events and to any (rather than specific) solicited systemic adverse events.

For unsolicited adverse events, imputations will be restricted to analyses of any adverse events and serious adverse events.

# 8.2.2 Immunogenicity Data

Missing immunogenicity values are considered MCAR and therefore will not contain information that impact the result of the analysis (i.e., not informative). Imputation methods will therefore not be used. The primary objectives will be analyzed using both the FAS and the PPS.

#### **8.3** Multicenter Studies

Vaccine group effects will be investigated first using a linear model which allows for center differences, but does not consider vaccine-by-center interaction, i.e., the model only considers effects for center and vaccine. A center effect will be included in all analyses of the primary and secondary objectives.

If the statistical model does not converge due to the factor "center", a model without center effect will be fitted instead.

The analysis of vaccine group effect split by center will be provided in Section 14 of the CSR for the primary objectives. If significant vaccine effects are found in a trial, there will be an exploration of the heterogeneity of vaccine group effects across centers. Results of vaccine by center interaction analysis will be provided in Appendix 16.1.9.

In case if center with low number of participants (e.g. N<= 5), country (Poland and Finland) will be used instead of center.

# 8.4 Multiple Comparisons and Multiplicity

Not applicable as there is only one primary hypothesis.

## 8.5 Immunogenicity/Safety/Other Subsets

Not applicable.

# 8.6 Subgroups

Analysis of the primary objective will be repeated and stratified by country, gender and race using the FAS and the PPS.

For details regarding the analyses by center please see section 8.3 above. Analyses by center will be presented in Section 14 of the CSR.

## 8.7 Data Transformation

Distributions of antibodies are generally skewed to the right (Nauta, 2010). Therefore, prior to any statistical analysis that assumes normally distributed observations, antibody titers or concentrations will be log10-transformed. GMTs [/GMCs] and their 95% CIs are computed by exponentiating (base 10) the least squares means and 95% CIs of the log10 titers.

# 8.8 Derived and Computed Variables

# Immunogenicity

Values below the limit of quantification (recorded as "< LQ") will be set to half that limit (i.e., LQ/2).

## Geometric Mean Titer/Concentration

The GMT will be calculated using the following formula:

$$10^{\left[\sum_{i=1}^{n}\log_{10}(t_{i})\atop n\right]}$$

where  $t_1, t_2, ..., t_n$  are *n* observed immunogenicity titers/concentrations.

## **Geometric Mean Ratio**

Geometric mean ratios (GMRs) measure the changes in immunogenicity titers/concentrations *within* subjects.

The GMR will be calculated using the following formula:

$$\begin{bmatrix}
\sum_{i=1}^{n} \log_{10} \binom{v_{ij}}{v_{ik}} \\
n
\end{bmatrix} = 10^{\begin{bmatrix}
\sum_{i=1}^{n} \log_{10} (v_{ij}) - \log_{10} (v_{ik}) \\
n
\end{bmatrix}}$$

where, for *n* subjects,  $v_{ij}$  and  $v_{ik}$  are observed immunogenicity titers/concentrations for subject *i* at time-points *j* and *k*,  $j \neq k$ .

#### 4-fold rise

The four-fold titer rise is defined as:

- for subjects with pre-vaccination hSBA titers <LLOQ, a post-vaccination hSBA

   ≥4 LLOQ;
- for subjects with a pre-vaccination hSBA titers ≥LLOQ, an increase of at least four times of the pre-vaccination hSBA.

(this definition is not in alignment with the protocol 2, 22 JUN 2016, as the protocol had a mistaken in the definition of 4-fold rise. A NTF is available at the time of approval of this SAP, and an amendement of protocol may be done in future to correct it).

#### Duration in the Study

**Duration in the study** is defined in days as:

Last visit date (visit x)a – Enrollment date (visit 1) + 1

aor premature discontinuation date (in case of withdrawal from the study)

The duration is missing if one of the dates is missing or incomplete.

# Solicited Adverse Events

For details see section 13.2.

# **Unsolicited Adverse Events**

All adverse events will be characterized according to the date of occurrence related to the vaccination phase as follows:

• Emergence before vaccination phase: start date before the first date of injection of study vaccine.

• Emergence during vaccination phase: start date on or after the first date of injection of study vaccine or, adverse event increase in severity including to "serious" adverse event.

If start date is equal to the first date of injection then "timing" variable ("On injection day, before injection"/"On injection day, after injection") will be used to define whether the adverse event occur before or after the injection.

If there are several vaccinations, the adverse event will be associated with the most recent vaccination.

If an adverse event start date is missing or unknown, the adverse event will be considered as emergent.

When start and/or end dates of an adverse event are only partially known, adverse events will be categorized as emergent before, during, or after vaccination phase using the following rules:

- If the partial end date is before (<) the first study vaccination (i.e., year or year & month is/are before the first study vaccination year or year & month) then the adverse event is emergent before vaccination phase.
- If the partial start date is equal or after (≥) the first study vaccination (i.e., year or year & month is/are after or the same as the first study injection year or year & month) then the adverse event is emergent during vaccination phase.

The **maximum event severity** is the greatest severity associated with a preferred term for a reported adverse event according to the following order: Mild < Moderate < Severe. Unknown/ Missing severity is considered as severe (except for the definition of emergence).

Multiple AEs with the same PT for the same subject are counted only once (except in occurrences tables produced for posting purposes).

**Vaccination-related Adverse Events** are those for which the cause has been evaluated by the investigator, and recorded either as possibly related, probably related or unknown/missing.

Safety Laboratory Data

Not applicable

# Prestudy, Concomitant and Post-Vaccination Medications

A **previous medication** is a medication used only before the first study vaccination (i.e. medication end date < first study vaccination date).

A **post-vaccination medication** is a medication used only after study termination (i.e. medication start date > study termination date).

All other medications are **concomitant**.

When start and/or end dates of a medication intake are missing, the medication is considered as concomitant with the study vaccination schedule.

If the first study vaccination date is missing then the medication is considered as concomitant with the study vaccination schedule, provided that the study vaccine was administered to the subject.

For further details please refer to the technical and program specifications document stored in Home/analysis/V102/V102\_15E1/purpose\_1/final/prod/docs and Home/analysis/V102/V102\_15E1/purpose\_1/adam\_1/prod/docs within the SAS Drug Development (SDD) server.

# 8.9 Analysis Software

All analyses will be performed using SAS Software version 9.2 or higher.

# 9. STUDY SUBJECTS

# 9.1 Disposition of Subjects and Withdrawals

All subjects who provide informed consent will be accounted for in this study. The frequencies and percentages of subjects in each analysis set, study withdrawals, subgroups, and major protocol deviations will also be presented.

The time the subjects are under observation will be summarized by vaccine and overall using summary statistics (mean, SD, minimum, median, maximum)

